7.2.3. Tertiary Analyses

Not applicable.

7.2.4. Other Efficacy Analyses

All exploratory analyses will be performed using the FA Set in the Treatment Period.

Assessment for each exploratory endpoint will be summarized for Baseline and post-baseline visits by descriptive statistics. Change from Baseline and percent change from Baseline (for plasma total and PUF Cu, cNCC, dNCC, LBC, Cp, and CpC only) will also be summarized for each post-baseline visits. In addition, following analyses will be done.

Endpoints with continuous outcome, which are measured multiple times between Baseline and Week 48, will be analyzed using the MMRM in the same manner as of CGI-S. Details of the MMRM can be referred to in Section [7.2.2](#).

- MELD
- Modified Nazer
- Plasma total and PUF Cu
- cNCC
- dNCC
- LBC
- Cp and CpC
- EQ-5D
- SF-36
- CLDQ
- BPRS-24
- FIB-4
- 24-hour Urine Cu/Mo/creatinine

For plasma total and PUF Cu, cNCC, dNCC, LBC, Cp, and CpC, additional MMRM model will be performed on percent change from Baseline.

For all exploratory endpoints with multiple measurements between Baseline and Week 48, the following plots will also be provided: mean and 95% CI plot over time, and spaghetti plot for patient level data over time.

For endpoints with continuous outcome that are only measured at Baseline and Week 48, a paired sample t-test on Baseline and Week 48 assessment values will be performed when data are available.

- Liver stiffness by MRE (kPA)
- Liver stiffness by transient elastography (kPA)
- Steatosis by MR-PDFF (percentage)
- Liver metals concentrations obtained from liver biopsy specimen

For endpoints with ordinal outcomes that are only measured at Baseline and Week 48, a Wilcoxon Signed-rank test will be used to compare Baseline versus Week 48 assessment values.

- TSQM-9
- UWDRS

The reference SAS code for a paired sample t-test and a Wilcoxon Signed-rank test can be found in Section 9.5.

For mitochondrial ultrastructure by electron microscopy and Cu deposition in the eye by optical coherence tomography, only by-patient listings will be provided.

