The principal aim of this study is to evaluate the effect of ALXN1840 on reduction of liver Cu concentration at Week 48 of treatment compared with baseline in patients with WD who have been previously treated with SoC (ie, trientine, penicillamine, or zinc) for at least 1 year. Molybdenum concentration will also be assessed in the liver.

Objectives and Endpoints

Objectives	Endpoints
Treatment Period	
Primary	
To evaluate change in liver copper (Cu) concentration following treatment with ALXN1840 at Week 48 in patients with Wilson disease (WD)	Change from baseline to Week 48 in liver Cu concentration
Secondary	
To assess change in liver histopathology following treatment with ALXN1840	Change from baseline to Week 48 in steatosis, inflammation, and fibrosis
To evaluate the safety of ALXN1840 in patients with WD	Adverse events (AEs), vital signs, ECGs, clinical laboratory data, and physical examination data
To evaluate pharmacokinetics (PK) of ALXN1840	
 ALXN1840 PK profiles in plasma at Week 6 (Day 43) and Week 36 (Day 253), of which ALXN1840 PK are measured as total molybdenum (Mo) and plasma ultrafiltrate (PUF) Mo Pre-dose trough ALXN1840 concentrations in plasma at each study site visit ALXN1840 concentrations in the liver biopsy specimen.
To evaluate the effects of ALXN1840 on clinical symptoms	Change from baseline in Clinical Global Impression-Improvement (CGI-I) Scale and the Clinical Global Impression-Severity (CGI-S) Scale
Exploratory	
To explore the effects of ALXN1840 on hepatic status	Change from baseline to Week 48 in: 
 Model for End Stage Liver Disease (MELD) score Modified Nazer score
To assess changes in liver fibrosis and steatosis using non-invasive techniques	Liver stiffness by magnetic resonance (MR) elastography and transient elastography (Vibration-Controlled Transient Elastography/FibroScan), MR-proton density fat fraction (PDFF)
To explore changes in mitochondrial ultrastructure of the liver at Week 48	Change from baseline to Week 48 in mitochondrial ultrastructure by electron microscopy
To explore the change in Cu deposition in the eye at Week 48	Change from baseline to Week 48 in in Cu deposition in the eye by optical coherence tomography

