3. OBJECTIVES AND ENDPOINTS

The study objectives and corresponding endpoints are presented in [Table 4](#).

Table 4: Study ALXN1840-WD-205 Objectives and Endpoints

Objectives	Endpoints
Treatment Period	
Primary	
To evaluate change in liver copper (Cu) concentration following treatment with ALXN1840 at Week 48 in patients with Wilson disease (WD)	Change from baseline to Week 48 in liver Cu concentration
Secondary	
To assess change in liver histopathology following treatment with ALXN1840	Change from baseline to Week 48 in steatosis, inflammation, and fibrosis
To evaluate the safety of ALXN1840 in patients with WD	Adverse events (AEs), vital signs, ECGs, clinical laboratory data, and physical examination data
To evaluate pharmacokinetics (PK) of ALXN1840	
 ALXN1840 PK profiles in plasma at Week 6 (Day 43) and Week 36 (Day 253), of which ALXN1840 PK are measured as total molybdenum (Mo) and plasma ultrafiltrate (PUF) Mo Pre-dose trough ALXN1840 concentrations in plasma at each study site visit ALXN1840 concentrations in the liver biopsy specimen.
To evaluate the effects of ALXN1840 on clinical symptoms	Change from baseline in Clinical Global Impression-Improvement (CGI-I) Scale and the Clinical Global Impression-Severity (CGI-S) Scale
Exploratory	
To explore the effects of ALXN1840 on hepatic status	Change from baseline to Week 48 in: 
 Model for End Stage Liver Disease (MELD) score Modified Nazer score
To assess changes in liver fibrosis and steatosis using non-invasive techniques	Liver stiffness by magnetic resonance (MR) elastography and transient elastography (Vibration-Controlled Transient Elastography/FibroScan), MR-proton density fat fraction (PDFF)
To explore changes in mitochondrial ultrastructure of the liver at Week 48	Change from baseline to Week 48 in mitochondrial ultrastructure by electron microscopy
To explore the change in Cu deposition in the eye at Week 48	Change from baseline to Week 48 in in Cu deposition in the eye by optical coherence tomography

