Liver biopsy for Cu concentration is considered the most effective means to show reduction in liver Cu; no other non-invasive surrogate marker is available to fully explore the impact of ALXN1840 on liver Cu stores. Although WD impacts patients of all ages, because it is a chronic disease, most treatment-experienced (ie, have received treatment for at least 1 year) patients are ≥ 18 years, therefore, including patients ≥ 18 years of age is representative of the population with WD.

To better understand the mechanism by which ALXN1840 results in reduction of liver Cu concentrations, the liver biopsy specimen will also be assessed for total Mo and concentrations will be correlated to blood total Cu and Mo concentrations.

In addition to evaluating liver Cu concentration, histology will be performed on the remaining liver tissue to assess the impact of ALXN1840 on liver inflammation and tissue injury, as well as progression in fibrosis.

Imaging (ie, magnetic resonance imaging [MRI] and transient elastography) will be performed to evaluate changes by non-invasive assessment of the liver. Optical coherence tomography will also be performed as a measure of Cu reduction with respect to Kayser-Fleischer rings.

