8.1.7. Imaging Techniques

Details of imaging techniques will be detailed in an Imaging Manual.

Magnetic Resonance Elastography and MR-PDFF

Baseline and follow-up MRI studies of the liver will be performed as detailed in the SoAs (Table 1 and Table 2) and read by a central radiologist with expertise in these methods. Hepatic steatosis will be quantified by magnetic resonance (MR)-proton density fat fraction (MR-PDFF). Hepatic stiffness will be quantitated by MR elastography (MRE) according to standard protocols.

Transient Elastography

Transient elastography (Fibroscan preferred) uses ultrasound and low-frequency elastic waves to quantify liver fibrosis. Vibration controlled transient elastography will be performed at visits as outlined in the SoAs (Table 1 and Table 2).

Optical Coherence Tomography

Optical coherence tomography uses light waves to map and measure the structures of the eye (Sridhar, 2017). Copper deposits in the anterior chamber of the eye will be photographed and quantitated at visits as outlined in the SoAs (Table 1 and Table 2).

Electron Microscopy

Electron microscopy enables examination of mitochondrial ultrastructure of the liver to determine whether hepatic mitochondrial function is affected negatively in WD (Einer, 2019).

The glutaraldehyde-fixed liver biopsy specimen will be processed by a qualified central laboratory to permit examination of subcellular ultrastructure using transmission electron microscopy and a descriptive assessment of electron microscopic images will be performed by an expert.

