9.4.1. Efficacy Analyses

9.4.1.1. Treatment Period

The primary objective of this study is to evaluate change in liver Cu concentration following treatment with ALXN1840 at 48 weeks in patients with WD. The primary analysis will be performed using the Full Analysis Set in the Treatment Period.

The change in liver Cu concentration will be evaluated using a paired samples t-test. For the primary analysis, a multiple imputation method will be used for missing data imputation.

Missing values for each patient will be imputed multiple times based on the estimated means from patients with similar baseline liver Cu concentration values. This approach will be used for all missing data at Week 48 due to any reason including, but not limited to, loss to follow-up and withdrawal of consent. The details of implementing this multiple imputation approach are as follows:

- Step 1: Missing values at Week 48 will be imputed 20 times via SAS PROC MI, using MCMC statement, including baseline and Week 48 liver Cu value; imputed values at Week 48 will be retained in the imputed datasets.
- Step 2: Apply paired samples t-test analysis for each of the 20 imputed datasets and save the mean and standard error at Week 48 from each of the 20 analyses.
- Step 3: Combine the 20 sets of analysis results via SAS PROC MIANALYZE. The combined treatment effect, confidence interval, and p-value will be estimated.

Sensitivity analyses will be performed to assess the robustness of the analysis result and will include:

- Use baseline value carried forward to impute missing Week 48 data
- Analyze primary endpoint using the Per Protocol Set, multiple imputation will be used to impute missing Week 48 data

Secondary and exploratory analyses will be performed using the Full Analysis Set in the Treatment Period.

For continuous endpoints that are measured multiple times between baseline and Week 48, data will be analyzed using mixed model repeated measures (MMRM) analysis. Fixed-effect terms will include visit and baseline value as covariates. An unstructured covariance will be used to model within-patient error.

For exploratory endpoints, data will be analyzed as observed, for endpoints that are only measured at baseline and Week 48, an analysis of covariance (ANCOVA) model will be used to analyze continuous endpoints, and a non-parametric ANCOVA model will be used to analyze ordinal outcomes. Baseline value will be included in the model.

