4.1. Changes From Analyses Specified in the Protocol

The following changes were made from analyses specified in the Protocol Amendment (approval dated 27 May 2022):

For exploratory endpoints measured only at Baseline and Week 48, a paired sample t-test or a Wilcoxon Signed-rank test will be used to assess Baseline and Week 48 results for continuous or ordinal outcomes, respectively, in this SAP per Section 7.2.4.

These analyses are to replace the ANCOVA or nonparametric ANCOVA models mentioned in Protocol Amendment 5 (approval date 27 May 2023) Section 9.4.1.1 for these endpoints.

4.2. Changes From Analyses Specified in the Previous Version of the Statistical Analysis Plan

The following updates have been made to the SAP version 1.0 approved on 16 Dec 2022:

Section No. and Name	Description of Change	Justifications
Section 3. Table 1. List of Abbreviations and Definitions of Terms	Added the following abbreviations: 
 • cNCC for calculated non-ceruloplasmin-bound Cu • dNCC for directly measured non-ceruloplasmin-bound Cu • AUEC_{0-48W} for daily mean AUEC of dNCC from 0 to 48 weeks • FIB-4 for Fibrosis-4 • PT for Preferred Term • ULOQ for upper limit of quantification 	To align with Protocol Amendment 5
Section 4. Description of the Protocol	Clarified that a liver biopsy is needed for patients entering Extension Period on Week 48 Clarified that all biopsy samples will be reviewed and scored by an independent expert hepatopathologist blinded to identity and biopsy order	To align with Protocol Amendment 5
Section 4.1. Changes From Analyses Specified in the Protocol	Added statements that ANCOVA or nonparametric ANCOVA models are replaced with a paired sample t-test or a Wilcoxon signed-rank test for continuous exploratory endpoints or ordinal exploratory endpoints tested only at Baseline and Week 48	To align with executed analysis and learnings for this study
Section 4.2. Changes From Analyses Specified in the Previous Version of the Statistical Analysis Plan	Provided summary of changes made in this SAP relative to SAP version 1.0 (approval date 16 Dec 2022)	Good documentation practice

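### Change in eye copper by optical coherence tomography is a stated exploratory endpoint with quantitated readings, but SAP 7.2.4 gives it listings only and SAP 4.1 does not declare this as a change

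*SAP*

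**What the plan says.** **Objective and endpoint.** Protocol Section 3, Table 4 gives the exploratory objective as "To explore the change in Cu deposition in the eye at Week 48". The matching endpoint is the change from baseline to Week 48 by OCT. Protocol 4.2 explains its purpose: "Optical coherence tomography will also be performed as a measure of Cu reduction with respect to Kayser-Fleischer rings".

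**Measurement.** Protocol 8.1.7 states: "Copper deposits in the anterior chamber of the eye will be photographed and quantitated at visits as outlined in the SoAs". The Treatment Period schedule (Protocol Table 1) marks OCT at Screening and at Week 48/Early Termination.

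**Analysis rule in the protocol.** For exploratory endpoints measured only at baseline and Week 48, Protocol 9.4.1.1 says "an analysis of covariance (ANCOVA) model will be used to analyze continuous endpoints, and a non-parametric ANCOVA model will be used to analyze ordinal outcomes".

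**Declared change in the SAP.** SAP 4.1 replaces those models for the same class of endpoints: "a paired sample t-test or a Wilcoxon Signed-rank test will be used to assess Baseline and Week 48 results for continuous or ordinal outcomes". It names no exception for OCT.

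**Analysis in the SAP.** SAP 7.2.4 opens with a general rule: "Assessment for each exploratory endpoint will be summarized for Baseline and post-baseline visits by descriptive statistics". It closes with a specific one: "For mitochondrial ultrastructure by electron microscopy and Cu deposition in the eye by optical coherence tomography, only by-patient listings will be provided". OCT appears in neither of that section's two lists of endpoints to be tested at two visits.

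**The concern.** The protocol asks a group-level question about change in eye copper and has patients scanned twice to answer it. The SAP then plans no mean or median change, no interval and no test. A reader of the study report would have to compute the summary from a listing.

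The departure could also pass without comment. Protocol 9.4 requires deviations from the analysis described in the SAP to be justified in the final report. Because listing-only is what the SAP describes, following it would trigger no explanation. SAP 4.1 is where the departure from the protocol should appear, and it is not there.

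What is at stake is one exploratory objective and the consistency of the plan. The liver copper conclusion is not at risk.

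**Working it through.** No planned figure exists for OCT, so the check is a comparison of texts.

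1. **Is it a change endpoint?** Yes, in Protocol Table 4. SAP 5.1.3 lists OCT without the word change, but it lists MR elastography, transient elastography and MR-PDFF in the same way, and SAP 7.2.4 still tests those three. The shorter wording therefore does not signal a listing-only intent.

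2. **Is it a two-visit endpoint in the Treatment Period?** Yes. Protocol Table 1 marks Screening and Week 48/ET, the same pattern as the other three imaging measures.

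3. **Is the reading numeric?** Protocol 8.1.7 says the deposits are quantitated. The same section calls the electron microscopy reading a descriptive assessment, so the protocol itself separates the two measures that SAP 7.2.4 puts in one sentence. However, SAP 5.1.3.3 gives a percentage for MR-PDFF and kPa for the two stiffness measures, but no variable, unit or scale for OCT. It refers to an imaging manual.

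4. **Which rules does the listing-only sentence meet?**

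| Rule | Covers OCT? | Met by listing only? |
|---|---|---|
| SAP 7.2.4, opening sentence (each exploratory endpoint summarised) | Yes, without condition | No |
| Protocol 9.4.1.1 (ANCOVA or non-parametric ANCOVA) | If continuous or ordinal | No |
| SAP 4.1 (paired t-test or Wilcoxon signed-rank) | If continuous or ordinal | No |
| SAP 4.1 as the record of changes from the protocol | Yes, if the protocol's rule covers OCT | Not declared |

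The first conflict holds whatever the scale. The others depend on the scale, which the documents do not give.

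5. **What would a summary provide?** The documents give no OCT variability, so precision can be stated only in units of the SD of the paired difference. The half-width of a 95% CI for a mean change is t(0.975, n−1)/√n:

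- n = 16: 2.131/4.000 = 0.53 SD
- n = 20: 2.093/4.472 = 0.47 SD
- n = 24: 2.069/4.899 = 0.42 SD
- n = 28: 2.052/5.292 = 0.39 SD

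The plan expects about 24 evaluable patients from about 28 enrolled; 16 and 20 are assumed lower values. These figures illustrate what the extra table would offer if the reading is continuous. The point does not depend on them.

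**The case against.** The strongest reply is that listing-only is a deliberate choice: SAP 7.2.4 names OCT and says so. The endpoint is exploratory, no multiplicity control applies, and a complete listing shows every patient, including those who worsen. The OCT variable is also undefined in both documents. MR elastography, transient elastography and MR-PDFF have stated units and OCT does not, so adding OCT to the test list without further work would prescribe a test on an unspecified quantity.

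Much of this stands. It limits the point to a minor one and means the fix must begin by defining the variable. It does not explain why the section contradicts its own opening sentence or why SAP 4.1 is silent.

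A second reply is that SAP 7.4 plans descriptive statistics of actual values and change from Baseline for efficacy endpoints in the Extension Period. Protocol 8.1.7 refers OCT timing to both schedules, but the Table 2 grid could not be read in the text available, so an extension scan is not confirmed. Even if there is one, it would not supply the Week 48 Treatment Period result.

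A reader might also infer more than the documents support:

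- **That every two-visit exploratory endpoint is owed a test.** The rules in Protocol 9.4.1.1 and SAP 4.1 cover continuous and ordinal outcomes only. Electron microscopy also has two visits and a change definition, and a listing is reasonable there.
- **That a known amount of power is being lost.** Any such figure would have to borrow the liver copper effect (228/319) for a different organ and method.
- **That OCT is the study's only direct measure of copper in tissue outside the liver.** Neither document says this.
- **That the listing would lead to selective reading of improvers.** This is speculation.

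**Conclusion.** The concern holds as an inconsistency in the plan that leaves a stated exploratory objective without a group-level estimate. The conflict within SAP 7.2.4 is unconditional. The conflict with Protocol 9.4.1.1 and SAP 4.1 holds on the assumption that the OCT reading is continuous or ordinal. The word quantitated in Protocol 8.1.7 makes that likely, but no section confirms it.

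The size is small: one exploratory endpoint, with no effect on the primary analysis. The number of informative pairs may fall below 24, because the inclusion criteria do not require Kayser-Fleischer rings and some patients may have no deposits at Baseline.

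**What to change.** In SAP 7.2.4:

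1. Remove OCT from the listing-only sentence.
2. State the OCT variable, its unit and how the two eyes are combined.
3. Summarise n, the number of patients with deposits at Baseline, and the Baseline, Week 48 and change values, with a 95% CI for the change.
4. Apply the two-visit test already in the SAP: paired t-test if the variable is continuous, Wilcoxon signed-rank if ordinal.
5. Keep listing-only for electron microscopy, and word the opening sentence so that it allows this exception.

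If the OCT readings prove non-numeric, keep the listing, but declare and justify it in SAP 4.1 as a departure from the protocol and except OCT from the opening sentence as well.

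The cost is a short SAP edit and one table from data already collected. The downside is one more unadjusted exploratory result.

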7.2.5. Pharmacokinetic and Pharmacodynamic Analyses

For PK and PD endpoints in the Treatment and Extension Periods, analyses will be performed using the respective PK and PD Analysis Sets, or FA Set in the Treatment and Extension Periods.

7.2.5.1. Pharmacokinetic and Pharmacodynamic Sampling

In the Treatment and Extension Periods, plasma samples will be obtained from the blood samples collected pre-dose on the day of all study visits. Patients will be instructed not to take their dose of ALXN1840 on the morning of scheduled study visits, so that PK/PD/biomarker samples are collected at pre-dose trough for measuring total and PUF Mo (PK), total and PUF Cu, cNCC/NCC_{corrected}, dNCC, LBC (PD), Cp, and CpC (biomarker). Additional measurements on ALXN1840 PK/PD including Mo and Cu in the tripartite complexes (TPCs) may be conducted.

In the Treatment Period, at the Week 6 (Day 43) and Week 36 (Day 253) Visits, serial blood samples will be collected for plasma PK/PD/biomarker concentrations at the following time points: pre-dose at 0 hour, and at 2- and 4-hours post-dose.

7.2.5.2. BLQ Values / Missing Values

For PK and PD parameter calculations, concentrations below the limit of quantification (BLQ) prior to the first measurable concentration will be set to 0; all other BLQ values will be treated as missing. For PUF Cu parameter calculations, all BLQ values will be set to 0.

For summary statistic calculations, plasma concentration values below the lower limit of quantification (LLOQ) will be set to the LLOQ for analyses using the FA Set and will be set to 0 for analyses using the PK Analysis Set.

For PD and biomarker summary statistic calculations, concentrations below the LLOQ will be set to the LLOQ for analyses using the FA Set and will be set to 0 for analyses using the PD Analysis Set.

7.2.5.3. Pharmacokinetic/Pharmacodynamic Data Presentation Conventions

Pharmacokinetic and PD concentration data will be summarized using the following descriptive statistics: number of patients (N), number of patients with available data (n), arithmetic mean, SD, arithmetic coefficient of variation (arithmetic CV), geometric mean (GM), GMCV, median, minimum, and maximum.

The pre-dose PD concentration will be used as Baseline; the absolute change from Baseline will be calculated as: a post-dose concentration value – Baseline concentration value; and the percent change from Baseline will be calculated as: $([\text{a post-dose concentration value} - \text{Baseline concentration value}] / \text{Baseline concentration}) \times 100\%$.

The following conventions will be applied to PK/PD presentations and summaries.

- For continuous variables, all mean and median values are formatted to 1 more decimal place than the measured value. SD values are formatted to 2 more decimal places than the measured value. Minimum and maximum values are presented with the same number of decimal places as the measured value.
- Date variables are formatted as DDMMYYYY for presentation. Time is formatted in military time as HH:MM for presentation.

